8.4.5.3 Renal impairment

If subsequent to study entry and while still on study therapy, a patient's estimated CrCl falls below the threshold for study inclusion (≥ 51 ml/min), retesting should be performed promptly.

A dose reduction is recommended for patients who develop moderate renal impairment (calculated creatinine clearance by Cockcroft-Gault equation or based on a 24 hour urine test of between 31 and 50 ml/min) for any reason during the course of the study: the dose of olaparib should be reduced to 100 mg twice daily.

No dose reductions for TMZ are required for moderate to severe renal impairment, although caution is advised in cases of CrCl < 36 ml/min. Because the CrCl determination is only an estimate of renal function, in instances where the CrCl falls to between 31 and 50 mL/min, the investigator should use his or her discretion in determining whether a dose change or discontinuation of therapy is warranted.

Olaparib has not been studied in patients with severe renal impairment (creatinine clearance ≤ 30 ml/min) or end-stage renal disease; if patients develop severe impairment or end stage disease it is recommended that study treatment be discontinued.

8.5 Pharmacokinetics

Pharmacokinetic parameters are not evaluated in this study.

8.6 Pharmacodynamics

Pharmacodynamic parameters are not evaluated in this study.

8.7 Genetics

8.7.1 Collection of optional genetic samples

If the patient agrees to participate in the optional genetic research study, a blood sample will be collected. Participation is optional. Patients who do not wish to participate in the genetic research may still participate in the study. In the event of DNA extraction failure, a replacement genetic sample may be requested from the patient. Signed informed consent will be required to obtain a replacement sample unless it was included in the original consent.

The blood and/or buccal swab sample for genetic research will be obtained from the patients at the screening visit. Although DNA variants are stable parameter, early sample collection is preferred to avoid introducing bias through excluding patients who may withdraw due to an adverse event (AE), such patients would be important to include in any genetic analysis. If for any reason the sample is not drawn at the screening visit, it may be taken at any visit until the last study visit.

Samples will be collected, labelled, stored and shipped as detailed in the Laboratory Manual.

8.7.2 Storage and destruction of genetic samples

The processes adopted for the coding and storage of samples for genetic analysis are important to maintain patient confidentiality. Samples may be stored for a maximum of 15 years or as per local regulations from the date of the patient's last visit, after which they will be destroyed. DNA is a finite resource that may be used up during analyses. The results of any further analyses will be reported either in the CSR itself or as an addendum or separately in a scientific report or publication.

No personal details identifying individual will be available to AstraZeneca or designated organizations working with the DNA.

8.8 Biomarkers

MGMT Promoter Hypermethylation Testing (integral biomarker):

Existing archival tumor biopsy samples will be used for pre-screening, and when slides are provided at least 10 unstained slides must be submitted. Methylation status of the human MGMT promoter on chromostome 10 will be performed in formal fixed paraffin embedded tissue, by sodium bisulfite conversion followed by multiplex PCR. The analysis will be performed in the CLIA certified pathology laboratory of [name] at Yale University School of Medicine in collaboration with [name] in the Yale Clinical Molecular Pathology Laboratory. Please refer to the Laboratory Services Manual for additional details regarding testing for MGMT Promoter Hypermethylation.

Exploratory biomarkers:

By participating in this study, the patient consents to the mandatory collection of tumor tissue (pre-treatment biopsy) and use of donated biological samples as described here. Tissue samples will be obtained from all screened patients.

Mandatory tumor and blood biomarkers to be evaluated to support the exploratory objectives of the study are described below. Alternative biomarkers may be evaluated as determined by additional data associated with disease progression/recurrence or response to the investigational treatment.

Biomarker assessments that may have the potential to identify patients likely to respond to treatment with olaparib and TMZ (determined from other studies with olaparib +/- TMZ) will be

investigated to determine a patient's biomarker status and for possible correlation with efficacy endpoints.

- Tumour biopsies will be taken at baseline and at progression for investigation of next generation sequencing profiling, patterns of DNA methylation and gene expression, γH2AX, changes in the immune composition of the tumor microenvironment, resistance mechanisms, and other exploratory endpoints to evaluate their association with the observed clinical responses to olaparib and TMZ.
- Please refer to the Central Laboratory Services Manual for further details regarding sample collection, shipping and storage.

Biomarkers will be tested in blood to evaluate their association with the observed clinical responses to olaparib and TMZ.

In addition, blood will be collected and an analysis may be performed on biomarker variants thought to play a role in DNA repair including, but not limited to, candidate genes/genome-wide analysis for RNA, serum analytes, or tissue biomarkers to evaluate their association with observed clinical responses to olaparib and TMZ.

Other samples may be used for research to develop methods, assays, prognostics and/or companion diagnostics related to MGMT promoter hypermethylation / silencing and DNA repair.

Any sample material remaining after completion of analyses to fulfil the study objectives may be used for optional exploratory research to develop methods, assays, prognostics, and/or companion diagnostics related to colorectal cancer, MGMT promoter hypermethylation / silencing, PARP, and DNA repair.

The biomarker data will have unknown clinical significance and the results will not be provided to patients, their family members, any insurance company or employer.

The exploratory biomarker plan is described by sample type below.

Fresh Tumor Tissue

A sample of fresh tumor tissue will be used to create colorectal carcinoma organoids and/or patient derived xenograft.

Whole blood gene expression

Whole blood samples will be obtained from all patients at the time points described in the SoA. The focus is likely to be given to the expression of DNA repair genes including but not limited to MGMT and immunomodulatory markers. Correlation with outcome data will be completed on select candidates, and predictive markers, with the aim of identifying useful expression thresholds for identifying patients likely to receive benefit.

Serum-based markers

Serum will be obtained to explore the expression of cytokines and chemokine.

Plasma-based markers (ctDNA, circulating soluble factors)

Plasma will be obtained from all patients as described in the SoAs. The concentration of a panel of relevant cytokines, chemokines, and other DNA damage and immune-related markers may be assessed. Plasma may also be used to evaluate mutant circulating tumor DNA. Overall mutational burden and/or somatic mutations/genomic alterations in plasma may be assessed using state-of-the-art methodologies. Such measurements may be correlated with response.

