CBC with differential	X	X ^g	X ^g	X ^g	X ^g		X ^g		X ^g		X ^g		X		
PT/INR and aPTT ^p	X														
Urinalysis	X	X													
CEA	X	X			X		X		X		X				
TSH	X ^h								X ^m						
EKG	X ⁿ														
Efficacy Measurement / Imaging															
CT Chest / Abdomen / Pelvis	X ⁱ	Response assessment imaging will be performed every 6 weeks (+/3 days) ^j										X ^k		X ^k	
Tumor Biopsies/Correlative Studies Blood															
Biopsy ^l	X												X		

Research Blood collection	X ^r	X	X	X	X		X		X				X	X	
Stool Sample	X ^q						X ^q								

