Data from the available pre-clinical studies and subsequent clinical development programme demonstrate that olaparib appears to be active and generally well tolerated in patients with solid tumors including those with *BRCA* mutated cancers. In ovarian cancer, responses have been seen in all patient groups, including platinum resistant and refractory cancer.

From the available data to date in patients with advanced cancer, there is no evidence of any unexpected toxicity following long-term olaparib (capsule) monotherapy exposure.

Adverse laboratory findings and/or clinical diagnoses considered to be causally associated with administration of olaparib monotherapy include haematological effects (anaemia, neutropenia, lymphopenia, thrombocytopenia, MCV elevation and increase in blood creatinine), nausea and vomiting, decreased appetite, diarrhea, dyspepsia, stomatitis, upper abdominal pain, dysgeusia,

fatigue (including asthenia), headache, dizziness and cough. Most of these events were generally mild or moderate in intensity.

In a relatively small number of patients, pneumonitis, MDS/AML and new primary malignancies have been observed. Evidence from across the development programme for olaparib does not support a conclusion that there is a causal relationship between olaparib and these events. These are important potential risks for olaparib and are being kept under close surveillance.

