9.4.3 Other analyses

Exploratory endpoints:

Genetic markers will be plotted using heat-maps and statistically compared across responders and non-responders using the Benjamini-Hochberg correction for multiplicity of p-values.

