9.4.4 Methods for multiplicity control

This is a single arm study with an integral biomarker therefore no adjustments for multiplicity are planned other than that mentioned in section 9.4.3 for the exploratory endpoints.

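### Whole-blood expression is to yield benefit thresholds, but the stated marker analysis has no term for leukocyte mix, so an association driven by blood counts can be read as a gene effect

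*Combined protocol and SAP*

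**What the plan says.** Under its whole-blood heading, section 8.8 states "Whole blood samples will be obtained from all patients at the time points described in the SoA". On content it says "The focus is likely to be given to the expression of DNA repair genes including but not limited to MGMT and immunomodulatory markers". Selected candidates are then correlated with outcome, "with the aim of identifying useful expression thresholds for identifying patients likely to receive benefit". The section does not name the time point that would supply a threshold.

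The analysis of markers is one sentence in 9.4.3, repeated in substance in the synopsis (1.2): "Genetic markers will be plotted using heat-maps and statistically compared across responders and non-responders using the Benjamini-Hochberg correction for multiplicity of p-values". Section 9.4.4 adds only that "no adjustments for multiplicity are planned other than that mentioned in section 9.4.3 for the exploratory endpoints". No section mentions leukocyte composition, cell-fraction adjustment or deconvolution for blood. The reference in 8.8 to immune composition concerns the tumour biopsy.

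Two other places bear on the point. Section 2.3.1 lists among effects causally associated with olaparib "haematological effects (anaemia, neutropenia, lymphopenia, thrombocytopenia, MCV elevation and increase in blood creatinine". Table 1 schedules a "CBC with differential", and Table 10 records total leukocytes, absolute neutrophils and absolute lymphocytes.

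**The concern.** RNA from unfractionated blood is a sum over cell types. A transcript that is more abundant in lymphocytes than in other leukocytes rises and falls with the lymphocyte fraction, even when expression per cell is the same in everyone. If that fraction also tracks outcome, the transcript will be associated with outcome with no gene-level difference behind it.

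Section 8.8 wants thresholds for recognising patients who benefit, and 8.8.1 foresees publication and pooling with other studies. A threshold that stands in for a routine blood count may not carry over to patients with different counts. It would also say nothing about MGMT silencing in the tumour, on which the trial is built. Benjamini-Hochberg controls for the number of tests; it does not correct a test that is biased by a shared covariate.

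**Working it through.** **Plan's own figures.** The documents give no figure for the blood-expression analysis. The design figures in 9.2 reproduce by exact two-stage calculation (significance level 0.0489, power 0.902, early stopping 0.630, expected size 16.8) and do not bear on this point.

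**Is the covariate available?** As Table 1 reads, research blood is drawn at nine points: screening, C1D1, C1D8, C1D15, C2D1, C3D1, C4D1, end of treatment and safety follow-up. The blood count with differential is scheduled at all of these except safety follow-up, so at eight of nine. Under footnote g, the count may be taken up to 24 hours before dosing in cycle 1 and up to 72 hours before dosing later.

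**Size of a pure composition effect.** Let f be the lymphocyte fraction and R the ratio of per-cell expression in lymphocytes to that in other leukocytes. Bulk expression is proportional to fR + (1 − f). For an assumed fall in f from 25% to 15% with no change per cell:
- R = 2: (0.30 + 0.85)/(0.50 + 0.75) = 1.15/1.25 = 0.92
- R = 3: (0.45 + 0.85)/(0.75 + 0.75) = 1.30/1.50 = 0.87
- R = 5: (0.75 + 0.85)/(1.25 + 0.75) = 1.60/2.00 = 0.80
- R = 10: (1.50 + 0.85)/(2.50 + 0.75) = 2.35/3.25 = 0.72

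**False-positive rate of the planned comparison.** Taken from the documents: 30 patients, and 4 responders (the success boundary) or 8 (25% × 30 = 7.5, rounded up). Assumed: mean lymphocyte fraction 25%, SD of log2 fraction 0.5, assay noise SD 0.4 log2, identical per-cell expression in all patients, and a correlation r between the fraction and the outcome underlying response. The test is responders versus non-responders at a nominal 5% per gene, with 5,000 simulated trials per setting.

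| Gene | Responders | r = 0.2 | r = 0.3 | r = 0.4 | r = 0.5 |
|---|---|---|---|---|---|
| Lymphocyte-only | 4 | 7% | 11% | 17% | 24% |
| Lymphocyte-only | 8 | 9% | 15% | 24% | 34% |

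Over the same values of r, a gene 2 times higher in lymphocytes gives 5-8% with either number of responders. A gene 3 times higher gives 6-11% with 4 responders and 6-13% with 8. Repeat runs moved the upper ends by about a point, hence the ranges 5-14% (2-3 times higher) and 7-35% (lymphocyte-only). With the fraction as a covariate the rate is 4-6% throughout.

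**Does Benjamini-Hochberg help?** A separate simulation used 100 genes with no per-cell difference, R of 1, 3, 5 or 10, 8 responders of 30, mean fraction 25% with SD 8 points, and residual SD 0.25 log2. The chance of at least one discovery after correction was 5% when responders and non-responders had the same fraction, 17% when they differed by 5 points and 60% when they differed by 10. With the log2 fraction as covariate it was 4-7%.

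**The case against.** The strongest reply is that the aim is prediction, not per-cell biology. If lymphocyte abundance tracks outcome, a transcript that carries it really is associated with outcome, and for immune markers an adjustment could remove the signal of interest. This stands as a reason not to replace the unadjusted result. It is no reason to omit the adjusted one, which shows whether the transcript adds anything to a blood count already in hand.

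It is also fair that the work is exploratory, that 8.8 calls the clinical significance unknown, and that the differential is collected anyway, so adjustment remains possible at analysis. That limits the severity.

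A reader might draw three stronger conclusions that the documents do not support:
- That the plan uses raw values or pools all visits. It says neither; it names no normalisation and no time point. A laboratory manual, not available here, covers sample handling.
- That the regimen's effect on blood counts must contaminate the thresholds. That effect cannot reach a sample taken before the first dose, where only baseline variation between patients remains. After dosing, even the net direction is not given: neutropenia raises the lymphocyte fraction and lymphopenia lowers it, and 2.3.1 lists both.
- That false positives run at 12-58% per gene. Such figures arise for a lymphocyte-only transcript tested against a continuous outcome, or for a gene 3-10 times higher in lymphocytes with a 5-10 point difference in fraction between responders and non-responders. Nothing in the documents says that MGMT or other DNA-repair genes behave that way.

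**Conclusion.** The point holds in a limited form. The plan seeks benefit thresholds from whole-blood expression, and its one stated marker test leaves out leukocyte composition, so a blood-count association can be reported as a gene effect. That requires both a transcript that differs by cell type and a cell mix that tracks outcome; without either, the test keeps about its nominal 5%. Under the assumptions above, the inflation is small for a gene 2-3 times higher in lymphocytes (5-14%) and material for a lymphocyte-only gene (7-35%). The fraction SD, the noise SD, the correlation with outcome and the cell-type ratios are all assumed, since the documents give none of them. The silence on which sample sets the threshold is a second gap, and it decides whether treatment effects on counts can enter at all. No primary or secondary result depends on this analysis.

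**What to change.** In 8.8 and 9.4.3:
- Derive any patient-selection threshold only from a sample drawn before the first dose (screening or C1D1).
- Report each whole-blood association twice: unadjusted, and adjusted for the lymphocyte fraction (or the log neutrophil-to-lymphocyte ratio) from the differential nearest to the research draw. Call a transcript a candidate marker only if it adds to the blood count.
- Label all thresholds hypothesis-generating, and state that whole-blood MGMT expression is not to be read as evidence of MGMT silencing in the tumour.

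The cost is a few sentences and no new data for the eight draws with a scheduled count. The adjustment uses one degree of freedom when there may be only 4 to 8 responders, so one composition covariate is about the limit. The nearest count may have been taken up to 24 hours before dosing in cycle 1, or 72 hours in later cycles, so the match is imperfect unless both tubes come from one draw. Table 10 lists no monocyte count, so the adjustment covers neutrophils and lymphocytes only.

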8.8.1 Storage, re-use and destruction of biomarker samples

Samples will be stored for a maximum of 15 years from the date of the last patient's last visit, after which they will be destroyed. The results of this biomarker research will be reported either in the CSR itself or as an addendum, or separately in a scientific report or publication. The results of this biomarker research may be pooled with biomarker data from other studies with the study drug to generate hypotheses to be tested in future research.

9. STATISTICAL CONSIDERATIONS

9.1 Statistical hypotheses

The primary objective of this study is to assess the efficacy of temozolomide in combination with olaparib in subjects with MGMT promoter hypermethylated advanced colorectal cancer who have progressed on at least one line of systemic chemotherapy by overall response rate as assessed per RECIST v.1.1. We hypothesize that the underlying response rate to the combination therapy is 25% or greater (H_1) compared to a null hypothesis of 5% (H_0) based on historical controls.

9.2 Sample size determination

The sample size estimation for the single-arm of this phase II study is based on the primary endpoint of objective response rate (ORR). The protocol plans to enroll a total of 30 evaluable patients at the recommended dose level in a single-arm open label phase 2 study Simon's Two-Stage optimal design. There will be screening for eligibility and we will examine several secondary endpoints. Patients will be considered evaluable for the primary endpoint if they complete at least 1 cycle of study treatment followed by response assessment imaging. Patients that are not evaluable may be replaced to ensure the appropriate number of evaluable patients is enrolled as outlined in the sample size determination for the primary endpoint in the Simon's two-stage optimal design described below.

Screen: To be eligible for this trial, patients will first need to be screened for the MGMT promoter hypermethylation and/or MGMT lack of expression. We anticipate at least 20% of those screened will exhibit an appropriate biomarker as well as meet eligibility criteria. To obtain 30 eligible patients, the mean number of patients to be screened is 150. Using the negative binomial distribution as reference, there is a 6% probability more than 190 subjects will need to be screened to attain the 30 eligible patients.

The **primary endpoint** is the objective response rate to the combined therapy and will be assessed in a Simon's two-stage optimal design. Published, historical records anticipate a response rate of 5% or lower and we will assume a null hypothesis of 5%. We will reject this null hypothesis in favor of a higher rate if we observe 4 or more responses in the evaluable patient sample of 30. Patients will be considered evaluable for the primary endpoint if they complete at least 1 cycle of study treatment with response assessment imaging. The trial will terminate early if we do not observe 1 or more responses in the first 9 evaluable patients. The probability of 4 or more responses in a sample of 30 has probability .049, which is the significance level. If the true, underlying response rate is 25% or greater, then this trial has power 90%. The expected sample size is 17 under the null hypothesis. There is a 63% chance of stopping early under the null hypothesis.

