Statistical methods

We anticipate about 20% of those screened will exhibit an appropriate biomarker as well as meet eligibility criteria. To obtain 30 eligible patients, the mean number of patients to be screened is 150. Using the negative binomial distribution as reference, there is a 6% probability more than 190 subjects will need to be screened to attain the 30 eligible patients.

The primary endpoint is the objective response rate to the combined therapy and will be assessed in a Simon's two-stage optimal design. Published, historical records anticipate a response rate of 5% or lower and we will assume a null hypothesis of 5%. We will reject this null hypothesis in favor of a higher rate if we observe 4 or more responses in the evaluable patient sample of 30. The trial will terminate early if we do not observe 1 or more responses in the first 9 evaluable patients. The probability of 4 or more responses in a sample of 30 is .049, which is the significance level. If the true, underlying response rate is 25% or greater, then this trial has a power of 90%. The expected sample size is 17 under the null hypothesis. There is a 63% chance of stopping early under the null hypothesis.

Secondary endpoints include overall survival, progression-free survival and toxicity. Survival endpoints will be plotted using the Kaplan-Meier, product-limit method and compared across clinical measurements using Cox proportional hazards regression. Time to progression begins at the time of initial treatment and ends at the earliest of withdrawal, diagnosed progression, or death. Toxicity rates will be compared to established rates for these treatments and summarized using means and 95% confidence intervals. Genetic markers will be plotted using heat-maps and statistically compared across responders and nonresponders using the Benjamini-Hochberg correction for multiplicity of p-values.

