4.2 Safety Evaluation Period

A safety evaluation period to assess for dose limiting toxicity (DLT) will be employed for at least the first 6 treated patients. Should excessive toxicity be observed at the starting dose, a dose de-escalation schema will be used for TMZ to 60 mg/m², while the olaparib will be maintained at the specified dose of 150 mg twice daily. Patients will be enrolled in cohorts of 3 during the safety evaluation period. For the first 3 patients treated on the study with olaparib 150 mg twice daily and TMZ 75 mg/m², if $\leq 1/3$ DLTs are observed, 3 additional patients will be enrolled at this dose and if $\leq 1/6$ DLTs are seen enrolment will proceed at this dose. If 2 or more DLTs are observed in either the first 3 or 6 patients treated at the starting doses, the TMZ dose will be decreased to 60 mg/m² with olaparib 150 mg twice daily. If 2 or more DLTs are seen in either the first 3 or 6 patients treated at TMZ 60 mg/m² with olaparib 150 mg twice daily then a further dose reduction to TMZ 50 mg/m² with olaparib 150 mg twice daily will be done. The doses of TMZ 50 mg/m² D1-7 with olaparib 150 mg twice daily have previously been tested as outlined in section 4.5. Therefore if the starting doses require reduction to TMZ 50 mg/m² D1-7 with olaparib 150 mg twice daily then safety will be assessed per the data safety monitoring plan as outlined in section 9.5.2.

The dose management tables throughout the protocol will be adjusted in an amendment as necessary if an alternate starting dose is identified. If a dose reduction is necessary, at least 9 patients (per early stopping rule) and up to 30 evaluable patients will be treated at the reduced dose as part of the efficacy analysis. Therefore in the case of a dose reduction the enrolment of 30 patients will be maintained at the same dose.

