9.3 Populations for analyses

Table 15.

Outcome variable	Populations
Efficacy Data	
ORR	Efficacy analysis set (ITT population)
PFS	Efficacy analysis set (ITT population)
OS	Efficacy analysis set (ITT population)
Safety Data	
AEs	Safety analysis set
ECOG performance status	Safety analysis set

AE Adverse events; ORR Overall response rate; PFS Progression free survival; OS Overall survival; ECOG Eastern Cooperative Oncology Group; ITT Intention to treat

All Subject Analysis Set

The All Subject Analysis Set will include information from all screened subjects, including those who did not meet the study entry criteria or did not receive a study treatment. This data set will only be used for disposition in which all screened subjects are accounted for.

Efficacy Analysis Set (ITT population)

The Efficacy Analysis Set will include all subjects who receive any amount of study treatment for efficacy analyses. Efficacy analyses will be based on the actual treatment received. The ORR analysis will be based on subjects who are in the Efficacy Analysis Set and who had disease assessment at baseline and at least 1 follow up disease assessment or subjects who died or

stopped treatment before the first scheduled disease assessment due to clinical progression or toxicity.

Safety Analysis Set

The Safety Analysis Set will include data from all subjects who receive any amount of study drug. Safety analysis will be based on the actual treatment received. All data will be included, and no subjects excluded because of protocol violations.

Schedule of Analysis

This is an open-label study. Ongoing analyses to help manage the study and support the DSMC reviews for safety and antitumor activity will be undertaken. A final analysis will be conducted after all subjects have completed the study.

Disposition

The number and percentage (n, %) of subjects enrolled, treated, lost to follow-up, and withdrawn from treatment or discontinued from the study (with reason) will be summarized. The sample sizes for the Efficacy Analysis Set, Safety Analysis Set will be clearly identified. All subjects in the All Subject Analysis Set will be included in the disposition analysis.

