9.4 Statistical analyses

We will use intention to treat (ITT) analysis for the primary and secondary endpoints.

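### The Simon go/no-go rules can drop and replace early treatment failures that the plan's own ITT response analysis keeps as non-responders

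*Combined protocol and SAP*

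**What the plan says.** **Decision rules.** Section 9.2 defines the set: "Patients will be considered evaluable for the primary endpoint if they complete at least 1 cycle of study treatment followed by response assessment imaging". It adds "Patients that are not evaluable may be replaced to ensure the appropriate number of evaluable patients is enrolled". The null is rejected on "4 or more responses in the evaluable patient sample of 30". The Synopsis gives the futility rule on the same set: "The trial will terminate early if we do not observe 1 or more responses in the first 9 evaluable patients". Sections 9.2 and 9.4.1 repeat it. Section 4.2 also plans in these terms after a dose reduction: "at least 9 patients (per early stopping rule) and up to 30 evaluable patients will be treated at the reduced dose".

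**Primary response rate.** Table 15 (Section 9.3) assigns ORR to the ITT population, defined as follows: "The Efficacy Analysis Set will include all subjects who receive any amount of study treatment for efficacy analyses". Section 9.4 states: "We will use intention to treat (ITT) analysis for the primary and secondary endpoints". The 9.3 text then narrows the ORR analysis to two groups. The first has a baseline and at least one later assessment. The second died, or "stopped treatment before the first scheduled disease assessment due to clinical progression or toxicity". Section 9.4.1 scores any missing assessment as non-response.

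**Replacement.** Section 7.3 says without qualification that withdrawn patients are not replaced. Section 6.3 applies this only once a cycle has been completed. Section 5.4 treats a patient who chooses to leave before completing cycle 1 as a withdrawal. Section 9.2 allows replacement of anyone not evaluable.

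**The concern.** A treated patient who dies or stops for clinical progression or toxicity, and has no response scan, is a non-responder under 9.3 and 9.4.1. Under 9.2 the same patient is not evaluable and may be replaced by someone who might respond. The decision rule thus removes likely failures that the reported ORR retains, and this can only favour a positive result if those patients truly do not respond. Because evaluable patients are recruited until there are 30, the ITT denominator can exceed 30, so the decision and the reported estimate can rest on different patients.

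The trial is open-label and response is investigator-assessed. The denominator should therefore be settled before response data accumulate.

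**Working it through.** **1. Reproduce the design.** Inputs from 9.2: first stage 9 patients, continue with at least 1 response; total 30, reject with at least 4; rates 5% and 25%. The rejection probability is

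P(p) = Σ over x = 1…9 of Bin(x; 9, p) × P(Y ≥ 4 − x), with Y ~ Bin(21, p).

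At p = .05:
- x = 1: .2985 × .0849 = .0254
- x = 2: .0629 × .2830 = .0178
- x = 3: .0077 × .6594 = .0051
- x ≥ 4: .0006

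The total is .0489 (plan: .049). Early stopping is .95^9 = .630 (plan: 63%). Expected N is 9 + 21 × .370 = 16.8 (plan: 17). At p = .25, power is .902 (plan: 90%). All four figures reproduce for exactly 9 and 30 patients in whichever set is tested.

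**2. Who is treated differently.** Section 8.1.2, Table 1 note k and the Synopsis ask for continued scanning after treatment stops without progression. The patients at issue are therefore those who do not complete cycle 1 or who have no response scan. The first scheduled scan is at the end of cycle 2 (Table 1, note j).

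| Treated patient | 9.2 decision | 9.3 ORR text | 9.4.1 |
|---|---|---|---|
| Death, clinical progression or toxicity before the first scheduled scan, none done | Out, replaceable | In | Non-responder |
| Withdraws with no scan | Out, replaceable | Left out | Non-responder |

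The second row is a further inconsistency, between 9.3 and 9.4.1.

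**3. Replacement of withdrawals.** Before completing cycle 1: 7.3 says no, while 6.3 (by implication) and 9.2 allow it. After cycle 1 but unscanned: 6.3 and 7.3 say no, while 9.2 allows it. For early death, progression or toxicity without withdrawal from the study, only 9.2 speaks, and it allows replacement.

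**4. Size.** Let f be the fraction of treated patients who are not evaluable. The documents do not give it, so 2 to 20% is an assumed range. Assume also that these patients are non-responders. If the all-treated rate is 5%, the evaluable rate is .05/(1 − f), which goes into the formula in step 1.

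| f | Evaluable rate | Type I error |
|---|---|---|
| 2% | .0510 | .052 |
| 5% | .0526 | .057 |
| 10% | .0556 | .067 |
| 20% | .0625 | .093 |

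If 5% was meant as an evaluable rate, the level stays at .049. The plan does not say which was meant.

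**5. Secondary illustration.** Section 9.4.1 plans a 95% Wilson interval. For 4/30 the lower limit is 5.3%. With two more unscanned failures, 4/32 gives 4.97%. At a true evaluable ORR of 25%, rejection together with an ITT interval that includes 5% occurs in about 0.6, 2.2, 3.9 or 5.0% of trials at f = 2, 5, 10 or 20%. At 5% the figures are about 0.5, 1.6, 2.9 and 3.5%.

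**The case against.** **The decision set is named.** A reader might infer that nobody knows which patients the 4-of-30 rule applies to. The documents do not support that: the Synopsis, 9.2 and the stop rule in 9.4.1 all say evaluable, and the rule applies to 30 such patients however many are treated. What stands is that 9.4 prescribes ITT for the primary endpoint without exception, and no passage confines ITT to estimation.

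**The interim wording in 9.5.** It speaks of the first 9 patients being evaluated and might be read as a different set. It refers back to 9.4, where the set is the first 9 evaluable patients. There is no conflict there.

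**The Wilson comparison.** A reader might infer that the plan's two outputs contradict each other at 4/32. Much of that is sidedness: the Simon level is one-sided and the interval two-sided, and the plan does not use the interval to decide. A 90% Wilson interval for 4/32 has a lower limit of 5.7% and first includes 5% at 4/37. With 5 responses, the 95% limit stays above 5% until n = 44. The comparison is an illustration and not the main evidence.

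**The fraction may be small.** Continued scanning after discontinuation, ECOG 0–1 and a life expectancy of at least 16 weeks all point to the lower end of the range. A patient who stops in cycle 1 could also still be scanned and respond. These points limit the size. They do not reconcile 9.2 with 9.3.

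**Conclusion.** The inconsistency is real and should be fixed. The go/no-go rule may drop and replace early failures that the plan's own primary analysis keeps. Section 9.3 disagrees with 9.4.1 on unscanned withdrawals, and 6.3, 7.3 and 9.2 disagree on replacing withdrawn patients.

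It would go too far to call the stated .049 wrong. It is exact for the tested set, and it understates type I error only if 5% is an all-treated rate. On that reading, with dropped patients as non-responders, the error is about .052 to .057 at f = 2 to 5%, .067 at 10% and .093 at 20%. The lower values are a modest excess, and the upper ones rest on a non-evaluable fraction that the documents neither state nor suggest.

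**What to change.** - **9.2:** amend the evaluability definition in both places it appears. For the Simon rules, patients treated at the dose carried forward under 4.2 who die, or stop for clinical progression or toxicity, before the first scheduled scan should count as non-responders and not be replaced. The Synopsis, 4.2 and the stop rule in 9.4.1 then follow through the term they already use. Section 9.5 needs no change.
- **9.3 and 9.4:** use this same set for the decision and the primary ORR. Say so explicitly, because 9.3 currently takes in anyone with any study treatment, including at a dose that was later abandoned. Make 9.3 agree with 9.4.1 that an unscanned withdrawal is a non-response.
- **6.3, 7.3 and 9.2:** give one replacement rule for efficacy. Leave replacement in the DLT cohort as it is.
- **Reporting:** give the ORR on the present 9.2 evaluable set as a sensitivity analysis, and state whether 5% and 25% are all-treated or evaluable rates.

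**Cost.** Wording only, with no new data. If 25% was meant as an evaluable rate, the rate in the tested set becomes .25 × (1 − f). Power falls from 90% to about 89, 88, 86 or 79% at f = 2, 5, 10 or 20%. False stopping at stage 1, (1 − rate)^9, rises from 7.5% to about 8.0, 8.7, 10.1 or 13.4%. If 25% is an all-treated rate, the stated 90% holds.
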